7.3 Vital Signs

Vital signs include blood pressure, heart rate, respiratory rate, and temperature.

Values and changes from baseline will be summarized at each scheduled visit with descriptive statistics. Both the change from Screening/Baseline (patient base) and the change from Flare-up Day 1 (flare-up based) will be presented. Mean values (+/- standard error) will be plotted over time for blood pressure and heart rate. If multiple records occur within a post-baseline visit, the first non-missing value will be used.

Potentially clinically significant values at baseline and new-onset PCS values post-baseline will be summarized with counts and percentages of subjects or flare-ups as appropriate. Separate analyses will be performed for the non-flare-up treatment visits and the flare-up treatment visits. New-onset PCS values are defined as values that were not PCS at baseline and were PCS post-baseline. PCS values are defined in Table 5.

Table 5. Potentially Clinically Significant Vital Sign Values

	PCS Low	PCS High
Systolic blood pressure	<86 mmHg or a decrease of ≥ 25 mmHg from baseline	>180 mmHg or an increase of ≥ 25 mmHg from baseline
Diastolic blood pressure	<48 mmHg or a decrease of ≥ 20 mmHg from baseline	>110 mmHg or an increase of ≥ 20 mmHg from baseline
Heart rate	<45 bpm or a decrease of ≥ 20 bpm from baseline	(1) >105 bpm AND an increase of ≥ 20 bpm from baseline (2) >125 bpm

mmHg = millimeters of mercury, bpm = beats per minute.

7.4 Body Weight

Values and changes from baseline will be summarized at each scheduled visit with descriptive statistics. Mean values (+/- standard error) will be plotted over time.

7.5 Knee and Hand/Wrist Radiograph

Subjects under the age of 18 years at the time of enrollment into Study PVO-1A-202 with open epiphyseal growth plates will undergo knee and hand/wrist radiographs (AP view) for assessment of epiphyseal growth plate.

Knee and hand/wrist radiographs will be performed remotely (eg, at a local medical facility) for subjects who are unable or unwilling to attend site visits. Once a subject has achieved 100% skeletal maturity (as confirmed by radiography), knee and hand/wrist radiographs will no longer be required. Summary statistics of bone age and chronological age (values and changes from baseline) will be calculated at each scheduled visit. Changes in bone age will be plotted over time.

Summary tables of growth plate abnormalities identified in radiographs will include the following:

- Number and percent of subject with epiphyseal growth plates open (by hand/wrist and/or knee).
- Number and proportion of subjects with any abnormality at each visit, for each specific abnormality (e.g. growth recovery lines, Sclerosis, Under mineralization, etc.).
- Number and proportion of subjects with any change from the prior timepoint for hand/wrist and knee by each abnormality for each visit.
- Number and proportion of subjects with any change from the prior timepoint for hand/wrist and knee by each abnormality across all post-screening visits. For summaries across all timepoints, the worst case for a given subject will be used in the analysis.
- Number and proportion of subjects with any change from the prior timepoint for hand/wrist and knee across all abnormalities and post-screening visits. For summaries across all abnormalities and timepoints, the worst case for a given subject will be used in the analysis.

7.6 Linear Growth Assessment

A linear growth assessment will be performed for subjects under the age of 18 years at the time of enrollment into Study PVO-1A-202 with open epiphyseal growth plates using stadiometry and knee height assessments.

7.7 Electrocardiogram

Values and changes from baseline will be summarized for continuous ECG parameters at each scheduled visit with descriptive statistics. Both the change from Screening/Baseline (patient based) and the change from Flare-up Day 1 (flare-up based) will be presented. If multiple records occur within a post baseline visit, the first non-missing value will be used.

Abnormal ECG categories will be assigned based on raw findings as shown in Table 6.

Table 6. Abnormal Electrocardiogram Categories

Abnormal ECG Category	Raw Findings
Rhythm	
 * Atrial premature complexes * Ventricular premature complexes * Sinus arrhythmia * Sinus tachycardia
Conduction	
 * Nonspecific intraventricular conduction delay * Right bundle branch block * Incomplete right bundle branch block * Left posterior fascicular block * Left bundle branch block * Incomplete left bundle branch block
Morphology/Chamber enlargement	
 * Left ventricular hypertrophy * Left ventricular hypertrophy with repolarization abnormality
Axis deviation	
 * Right axis deviation * Left axis deviation
Myocardial infarction	
 * Pathologic Q waves * Acute ST elevation MI * Acute non-ST elevation MI
ST Segment/T Waves/U Waves	
 * Early repolarization * Nonspecific ST and T wave abnormality * Nonspecific ST elevation * Nonspecific U wave abnormalities
Miscellaneous	
 * Long QT interval * Short PR interval

Overall interpretation and abnormal ECG categories will be summarized at each scheduled visit with counts and percentages of flare-ups. New-onset ECG abnormalities are defined as

abnormalities that did not exist at baseline. New-onset ECG abnormalities will be summarized counts and percentages of subjects or flare-ups as appropriate.

Incidence of QTc >450 msec, QTc >500 msec, or change from baseline in QTc >60 msec will be summarized with counts and percentages of subjects or flare-ups as appropriate.

Potentially clinically significant values at baseline and new-onset PCS values post-baseline will be summarized with counts and percentages of subjects or flare-ups as appropriate. New-onset PCS values are defined as values that were not PCS at baseline and were PCS post-baseline. PCS values are defined in Table 7.

Table 7. Potentially Clinical Significant Electrocardiogram Values

	PCS Low	PCS High
PR interval	N/A	>200 msec or an increase from baseline of ≥ 20 msec
QRS interval	N/A	>100 msec or an increase from baseline of ≥ 10 msec
QT interval, QTcF, QTcB	N/A	>500 msec or an increase from baseline of ≥ 60 msec

msec = millisecond, QTcF = rate-corrected QT interval using Fridericia's formula (QT interval divided by the cube root of the RR interval), QTcB = rate-corrected QT interval using Bazett's formula (QT interval divided by the square root of the RR interval)

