6.2.13 Bone, Cartilage, Angiogenesis, and Inflammation Biomarkers

Blood and urine samples will be collected for cartilage, bone, angiogenesis, and inflammation. Bone and cartilage biomarkers include osteocalcin, bone specific alkaline phosphatase (B-ALP), procollagen type I C-terminal propeptide (PICP), procollagen 1 N-terminal propeptide (PINP), CD retinoic acid-sensitive protein (CD-RAP), and C-terminal telopeptide (CTX). The angiogenesis biomarker is the ratio of fibroblast growth factor and urine creatinine. Inflammation biomarkers include erythrocyte sedimentation rate (ESR), C reactive protein (CRP), interleukin 6 (IL-6), interleukin 1 beta (IL-1 beta), tumor necrosis factor (TNF), creatine kinase (CK), and lactate dehydrogenase (LDH).

Biomarkers values and changes from baseline will be summarized at each scheduled visit with descriptive statistics. Note that results obtained locally rather than from the central laboratory will not be used to calculate change from baseline and will be excluded from these summaries. Results captured as “<” or “>” will be rounded up or down accordingly for analysis (eg, “<0.61” will be rounded to 0.60).

Abnormal values at baseline and new-onset abnormal values post-baseline will be summarized with counts and percentages of flare-ups. New-onset abnormal values are defined as values from biomarkers that were normal at baseline and abnormal post-baseline or were abnormal at baseline and abnormal in the opposite direction post-baseline (eg, abnormal low at baseline and abnormal high post-baseline). Note that results obtained locally will be included in these summaries.

The following figures will be generated (note that the unit of analysis is each flare-up):

- Mean biomarker values over time (one figure per biomarker, each figure with one line).
- Mean biomarker values over time by incidence of new HO (one figure per biomarker, each figure with one distinctive line per subgroup [new HO, no new HO]).
- Mean biomarker values over time by baseline edema status (one figure per biomarker, each figure with one distinctive line per subgroup [baseline edema present, baseline edema not present]).

- Biomarker values over time by flare-up (one figure per biomarker, each figure with one distinctive line per flare-up). Flare-ups will be identified in the legend with subject ID, flare-up identifier (eg, Flare A, Flare B), gender, and age.

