3.3 Definition of New-Onset Potentially Clinically Significant (PCS) Value

New-onset potentially clinically significant (PCS) values are defined as values that were not PCS at baseline and were PCS at post-baseline.

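### The new-onset PCS counts for ECG and vital signs leave out further worsening in anyone already past the absolute limit at baseline

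*SAP*

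**What the plan says.** In Part B, Table 7 (section 7.7) sets the ECG limits as alternatives: PR ">200 msec or an increase from baseline of" at least 20 msec, QRS ">100 msec or an increase from baseline of" at least 10 msec, and QT, QTcF and QTcB ">500 msec or an increase from baseline of" at least 60 msec. Table 5 (section 7.3) does the same for blood pressure. Systolic low, for example, is "<86 mmHg or a decrease of" at least 25 mmHg. Heart rate high differs: it is either above 105 bpm together with a rise of at least 20 bpm, or above 125 bpm.

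Section 7.7 says what is tabulated: "Potentially clinically significant values at baseline and new-onset PCS values post-baseline will be summarized with counts and percentages of subjects or flare-ups as appropriate". It defines the second of these: "New-onset PCS values are defined as values that were not PCS at baseline and were PCS post-baseline". Section 7.3 uses the same definition for vital signs.

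The Part C SAP repeats the rule in section 3.3 ("values that were not PCS at baseline and were PCS at post-baseline") and applies it in 7.3 and 7.6. The Part A SAP has it in 8.3 and 8.7.

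In all three parts, QTc changes above 60 msec are also counted, with no condition on baseline PCS status. No matching row is planned for PR, QRS, uncorrected QT or blood pressure.

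**The concern.** The change criterion exists to pick up large individual shifts whatever the starting value. The new-onset rule disables it for subjects who start beyond the absolute limit, for example those who enter with slow conduction or low blood pressure. They appear once as PCS at baseline, and no later deterioration, of whatever size, moves them into another cell. A reader of the table cannot tell a stable pre-existing abnormality from one that worsened markedly on drug.

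Baseline in the flare-up-based safety tables makes this more relevant. Under Part B section 7 that baseline is Flare-up Day 1, and some Adult Cohort subjects are by then already on daily non-flare-up treatment (section 2.4). A value that passed a limit during that treatment counts as PCS at baseline, so worsening on the flare-up regimen drops out of the flare-up-based new-onset count.

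A second, smaller point is that the rule does not say whether PCS low and PCS high are judged separately when baseline status is set.

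**Working it through.** The SAP states no figure on this point, so there is none to reproduce. The check has two steps.

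**Step 1: apply the rule as written.** Inputs are the limits in Part B Tables 5 and 7 and the new-onset definition. For an ordinary high criterion, with baseline b, post-baseline value x, limit L and change threshold d:

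- PCS at baseline: b > L, because the change term is b − b = 0.
- PCS post-baseline: x > L or x − b ≥ d.
- New-onset: not PCS at baseline, and PCS post-baseline.

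If b > L, new-onset is false for every x. Low criteria mirror this. Illustrative pairs:

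| Parameter | Baseline → post | Change | PCS at baseline | New-onset |
|---|---|---|---|---|
| QRS | 95 → 106 msec | +11 | no | counted |
| QRS | 102 → 142 msec | +40 | yes | not counted |
| PR | 190 → 215 msec | +25 | no | counted |
| PR | 205 → 265 msec | +60 | yes | not counted |
| QT or QTc | 505 → 575 msec | +70 | yes | not counted; QTc is caught by the separate >60 msec row |
| QT or QTc | 505 → 565 msec | +60 | yes | not counted; QTc also missed by the >60 msec row |
| Systolic BP | 182 → 215 mmHg | +33 | yes | not counted |
| Systolic BP | 84 → 58 mmHg | −26 | yes | not counted |
| Diastolic BP | 112 → 135 mmHg | +23 | yes | not counted |
| Diastolic BP | 47 → 26 mmHg | −21 | yes | not counted |
| Heart rate | 110 → 132 bpm | +22 | no | counted |
| Heart rate | 126 → 150 bpm | +24 | yes | not counted |
| Heart rate | 44 → 24 bpm | −20 | yes | not counted |

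Heart rate from a baseline of 106 to 125 bpm is still counted, because that branch needs the limit and the rise together and so is not met at baseline.

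**Step 2: size, for QRS only, on assumptions.** The documents give no means, SDs or baseline prevalence. Assume a mean μ of 85, 90 or 95 msec, between-subject SD 10, within-subject SD 4 and a uniform drug effect δ. Then:

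- Baseline B has SD √(10² + 4²) = 10.77.
- Change D has mean δ and SD √2 × 4 = 5.66.
- Corr(B, D) = −4² / (10.77 × 5.66) = −0.26.
- Share lost = P(B > 100 and D ≥ 10) / P(D ≥ 10).

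With δ = +15, P(D ≥ 10) = P(Z ≥ (10 − 15)/5.66) = 81.2%.

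| μ (msec) | P(B > 100) | P(B > 100 and D ≥ 10) | Share of rises lost |
|---|---|---|---|
| 85 | 8.2% | 5.4% | 5.4/81.2 = 6.7% |
| 90 | 17.7% | 12.3% | 12.3/81.2 = 15.1% |
| 95 | 32.1% | 23.4% | 23.4/81.2 = 28.8% |

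With δ = +5 the loss is 3% to 19% of rises; with δ = 0 it is 2% to 14%.

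For scale, Part B plans about 60 subjects. If 2%, 5%, 10% or 20% were PCS at baseline on one parameter (assumed values), 60 × p = 1.2, 3, 6 or 12 subjects could not contribute a new-onset event on it.

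**The case against.** A new-onset count that excludes pre-existing abnormality does what its name says, and these are descriptive tables in an open-label extension. The biomarker rule in Part B section 6.2.13 follows the same logic. It adds a value only where results "were abnormal at baseline and abnormal in the opposite direction post-baseline", and it too ignores further worsening in the same direction. That is fair as a defence of the label, but it does not explain why the tables have no place for a change that the SAP itself classes as potentially significant.

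A reader might infer that such worsening is never seen at all. The documents do not support that:

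- Changes from baseline are summarised for all subjects.
- New-onset ECG findings, including conduction delay and bundle branch block, are counted separately.
- All Part B data are listed, and Part C lists every subject meeting PCS ECG criteria.
- QTc has its own change row.

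What remains is narrower: for PR, QRS, uncorrected QT and blood pressure, no threshold-based count of change includes subjects who were PCS at baseline. Means dilute individual shifts, and listings give no incidence.

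A reader might also infer a large loss for systolic pressure, because a low baseline could block a later PCS-high rise. This needs PCS status to be judged across directions, whereas Table 5 has separate low and high columns and the text is at most ambiguous. Most such rises would also be regression to the mean after a chance low reading, not harm. No systolic figure is offered here.

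Finally, the +15 msec effect is an assumption, and a shift that large would show in the mean-change table. That stands; the percentages are illustrative.

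**Conclusion.** The point holds as a limitation of the new-onset PCS tables in all three parts. As written, the change criterion cannot operate for anyone past the absolute limit at baseline. Further worsening in PR, QRS, uncorrected QT, blood pressure, and heart rate from above 125 or below 45 bpm is therefore left out of these counts. QTc is covered except for a change of exactly 60 msec, because one row uses at least 60 and the other more than 60.

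The mechanism follows from the text and needs no assumption; its size does. The QRS range of about 7% to 29% of rises of at least 10 msec depends on the assumed distributions and the +15 msec effect, and falls to 3% to 19% at +5 msec. The documents do not allow a firmer figure. The change should be made because it corrects an undercount in a safety table at little cost, not because a large loss has been shown.

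**What to change.** Amend Part B 7.3 and 7.7, Part C 3.3, 7.3 and 7.6, and Part A 8.3 and 8.7 as follows:

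1. Count the change criterion whenever the post-baseline change meets its threshold, whatever the baseline PCS status. Show it in its own row, or use a shift table of baseline against worst post-baseline value.
2. Keep the condition of a non-PCS baseline for the absolute limit only.
3. State that PCS low and PCS high are judged separately, at baseline and afterwards.

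The cost is a few lines of SAP text and a small derivation change; no new data are needed. PCS counts will rise slightly. Some of the added changes will be a return towards normal, such as a rise from a low blood pressure. A separate row or a shift table keeps these visible so that they are not read as deterioration.

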7.8 Physical Examination

Physical examination results will be summarized at each scheduled visit by body system with counts and percentages of subjects or flare-ups as appropriate.

7.9 Columbia-Suicide Severity Rating Scale

Suicidal ideation and behavior will be assessed using the Columbia-Suicide Severity Rating Scale (C-SSRS).

Data listings will be provided for (1) all C-SSRS results; and (2) for subjects reporting any type 4 or type 5 suicidal ideations.

8 Pharmacokinetics Data

Pharmacokinetics will be assessed within 7 days of flare-up based treatment initiation and at the end of treatment for the first treated flare-up. Blood samples will be taken at 0, 3, 6, 10, and 24 hours post-dose.

Plasma palovarotene concentrations will be summarized with descriptive statistics (number of non-missing values, arithmetic mean, standard deviation, standard error, coefficient of variation, geometric mean, median, minimum, and maximum). All plasma concentrations below the limit of quantification (LOQ) will be set to zero for the purpose of calculating descriptive statistics. If

at any time point, 1/3 or more of subjects have <LOQ values, descriptive statistics will not be calculated at that time point. PK concentrations will be imputed using the following:

- If 0-hour concentration missing, then 24-hour concentration used to replace the missing concentration.
- If 24-hour concentration missing, then 0-hour concentration used to replace the missing concentration.
- Invalid 24-hour concentrations were replaced with the 0-hour concentrations. Twenty-four-hour concentrations were determined to be invalid if concentration is greater than the 10-hour value (i.e. assumed to have been obtained after next day dose instead of before next day dose).

If any other blood sample collections are missing, PK parameters will not be assessed. Actual sampling times will be used for the PK analysis, if available. Nominal sampling times will be used for descriptive statistics.

Individual concentration-time profiles for palovarotene will be presented (linear and semi-logarithmic scales). Arithmetic means (+/- standard deviation) concentration-time profiles will also be presented (linear and semi-logarithmic scales).

An exploration of the effects of body weight on PK will be performed as the data allow.

The PK analysis of palovarotene will be conducted using model-independent methods as implemented in WinNonlin™. The PK variables analyzed will include $AUC_{0-24(ss)}$, $C_{max(ss)}$, $C_{min(ss)}$, $T_{max(ss)}$, CL/F , λ_z , and $t_{1/2z}$ at steady-state. The PK variables are defined as follows:

$AUC_{0-24(ss)}$	Area under the concentration versus time curve over the 24-hour dosing interval; calculated using linear trapezoid rule.
$C_{max(ss)}$	Maximum or peak measured plasma concentration at steady-state.
$C_{min(ss)}$	Minimum or trough measured plasma concentration at steady-state.
$T_{max(ss)}$	Time of maximum or peak measured plasma concentration at steady-state, obtained by inspection.
CL/F	Clearance defined as: $Dose/AUC_{0-24(ss)}$.
λ_z	Terminal rate constant
$t_{1/2z}$	Apparent terminal elimination half-life; calculated as $\ln(2)/\lambda_z$. The number of data points included in the regression will be determined by visual inspection, but a minimum of three data points in the terminal phase, excluding C_{max} , will be required to estimate λ_z .

9 Changes from Protocol

For the purposes of clarity and consistency of nomenclature, the Flare-up Rate Population described in the protocol was renamed as the Non-Flare Treated Population.

The initial secondary objective listed in Section 2.1.2 was not included in Amendment 3 of the protocol for Study PVO-1A-202 Part B or Amendment 1 of the protocol for Study PVO-1A-204.

The protocol describes the primary comparison of outcomes to be from data collected from the NHS and Phase 2 study. These comparisons will be performed in a future analysis and the analysis described here will instead focus on comparisons solely from Study PVO-1A-202 Part B between treatment groups of PVO 20/10 mg and Prior Non-Flare-up/PVO 20/10 mg, for flare based analyses; and treatment groups of treated, untreated, or no-flares, for WBCT based analyses.

10 References

3. D'Agostino, RB., Jr., Tutorial in Biostatistics: Propensity Score Methods for Bias Reduction in the Comparison of a Treatment to a Non-Randomized Control Group. *Statistics in Medicine*, 1998, 17, 2265-2281.

Appendices

Appendix 1. PROMIS T-Score Conversions

The following conversion tables allow a user to convert Global Physical Health, Global Mental Health, and Total scores into T-scores. T-score distributions are standardized such that a 50 represents the average (mean) for the US general population, and the standard deviation around that mean is 10 points. A high score always represents more of the concept being measured. Thus, a subject who has a T-score of 60 is one standard deviation better (more healthy) than the general population.

Adult Global Physical Health		
Raw Score	T-Score	Standard Error
4	16.2	4.8
5	19.9	4.7
6	23.5	4.5
7	26.7	4.3
8	29.6	4.2
9	32.4	4.2
10	34.9	4.1
11	37.4	4.1
12	39.8	4.1
13	42.3	4.2
14	44.9	4.3
15	47.7	4.4
16	50.8	4.6
17	54.1	4.7
18	57.7	4.9
19	61.9	5.2
20	67.7	5.9

Adult Global Mental Health		
Raw Score	T-Score	Standard Error
4	21.2	4.6
5	25.1	4.1
6	28.4	3.9
7	31.3	3.7
8	33.8	3.7
9	36.3	3.7
10	38.8	3.6
11	41.1	3.6
12	43.5	3.6
13	45.8	3.6
14	48.3	3.7
15	50.8	3.7
16	53.3	3.7
17	56.0	3.8
18	59.0	3.9
19	62.5	4.2
20	67.6	5.3

Pediatric Self-Completed Total		
Raw Score	T-Score	Standard Error
7	16.0	3.4
8	17.1	3.6
9	18.3	3.7
10	19.7	3.8
11	21.2	3.8
12	22.8	3.7
13	24.4	3.6
14	26.1	3.6

Pediatric Proxy-Completed Total		
Raw Score	T-Score	Standard Error
7	14.7	2.9
8	15.3	3.1
9	16.0	3.2
10	16.9	3.4
11	18.1	3.6
12	19.4	3.7
13	21.0	3.8
14	22.7	3.8

Pediatric Self-Completed Total			Pediatric Proxy-Completed Total		
Raw Score	T-Score	Standard Error	Raw Score	T-Score	Standard Error
15	27.6	3.5	15	24.4	3.7
16	29.2	3.5	16	26.1	3.7
17	30.8	3.5	17	27.7	3.7
18	32.4	3.6	18	29.4	3.8
19	34.0	3.6	19	31.2	3.8
20	35.6	3.6	20	32.9	3.8
21	37.2	3.6	21	34.6	3.8
22	38.8	3.6	22	36.2	3.8
23	40.4	3.6	23	37.9	3.9
24	42.1	3.7	24	39.7	4.0
25	43.9	3.7	25	41.7	4.0
26	45.7	3.6	26	43.6	3.9
27	47.5	3.6	27	45.4	3.8
28	49.2	3.6	28	47.3	3.9
29	51.1	3.7	29	49.3	4.1
30	53.3	3.9	30	51.8	4.4
31	55.7	4.2	31	54.5	4.7
32	58.3	4.5	32	57.3	5.0
33	61.1	4.9	33	60.2	5.4
34	64.2	5.4	34	63.2	6.0
35	67.5	6.1	35	66.1	6.5

Statistical Analysis Plan

A Phase 2, Open-Label Extension, Efficacy and Safety Study of a RAR γ -Specific Agonist (Palovarotene) in the Treatment of Preosseous Flare-ups in Subjects with Fibrodysplasia Ossificans Progressiva (FOP)

Study Number: PVO-1A-202 Part C

Original Protocol: 04 June 2014
Amendment 1: 30 September 2014
Amendment 2: 22 June 2015
Amendment 3: 10 March 2016
Amendment 4: 01 September 2017
Amendment 5: 06 June 2018
Amendment 6: 08 March 2019
